1.0 Objectives

1.1 Primary Objectives:

- 1.1.1 To evaluate the efficacy of levocarnitine in combination with vitamin B complex in treating PEG-asparaginase or inotuzumab ozogamicin induced hyperbilirubinemia (total bilirubin >3 xULN) in patients with ALL.

1.2 Secondary Objectives

- 1.2.1 To evaluate chemotherapy dose intensity in patients treated with PEG-asparaginase or inotuzumab ozogamicin
- 1.2.2 To characterize the safety, tolerability, and adverse event profile of levocarnitine and vitamin B for the treatment of hyperbilirubinemia.

2.0 Background

2.1 PEG-asparaginase hepatotoxicity in adult patients with acute lymphoblastic leukemia (ALL).

Despite exceptionally high rates of survival in pediatric patients with ALL of greater than 90%, adult patients continue to have markedly inferior outcomes^{1,2}. As age at diagnosis increases, survival decreases to a rate of less than 20% for patients over the age of 60 treated in the United States². This large disparity in outcomes is likely multifactorial and may be due to the fact that adult patients more frequently have worse genetic aberrations at diagnosis in addition to comorbidities which result in poor tolerability and dose reduction of cytotoxic chemotherapy or elimination of certain agents completely. *E. coli* L-asparaginase is an agent that is effective in the treatment of pediatric ALL, but has traditionally been omitted from adult treatment regimens due to poor tolerability. The unique side effect profile of L-asparaginase includes infusion-related reactions, hyperglycemia, hypertriglyceridemia, thrombosis and hemorrhage, hepatotoxicity, and pancreatitis³. A higher incidence of hepatotoxicity in addition to hyperglycemia, and hypofibrinogenemia has been reported in adult patients treated with asparaginase, compared to the pediatric population³. PEG-asparaginase (PEG) is the pegylated version of *E. coli* L-asparaginase and has replaced the original formulation, *E. coli* L-asparaginase, on the United States market. While pegylation of the product results in a prolonged half-life and less frequent dose administration, toxicities can be observed for a prolonged period of time after drug administration. Hepatotoxicity is a particularly difficult toxicity to manage and has played a large role in limiting the use of PEG in adult patients. Unlike other side effects such as thrombosis, bleeding and hyperglycemia that can be directly managed through supportive care treatments, hepatotoxicity lacks such treatments. Furthermore, severe hepatotoxicity itself can cause alterations in bleeding and clotting, ascites, renal dysfunction, treatment delays leading to increased morbidity and mortality especially in the setting of neutropenia⁴. Historical experience with PEG in adult patients (median 42 yo, range 22-69) at our institution resulted in 41% of patients experiencing grade ≥ 3 hyperbilirubinemia; and 51% of patients unable to complete their intended therapy, largely due to hepatotoxicity⁵. Even in a younger cohort of patients (median age 21), 38% of patients experienced hyperbilirubinemia when treated with PEG as part of a separate protocol⁶. Outside institutions have also reported similar rates of hepatotoxicity, ranging from 10%-37%, in adult patients

treated with PEG^{4,7-9}. The high rates of hepatotoxicity limit the use of PEG in adults, therefore, assessing the efficacy of supportive therapy for its management is warranted.

Although hyperbilirubinemia is frequently reported in adult patients treated with PEG, determining risk factors associated with severe hyperbilirubinemia has been challenging due to the variations in protocols. Amongst the published protocols with PEG, there are differences in patients' age, stage of treatment, doses and frequency, and concomitant medications (e.g. anthracyclines). These variations have led to discrepancies in the reported incidence of hyperbilirubinemia. Age has traditionally been considered a risk factor for hyperbilirubinemia due to the poor tolerance among the adult patient population. Age cutoffs of both 40 and 45 years have been associated with increased induction mortality and toxicity in PEG-containing protocols^{4,5}. However, Douer et al. successfully administered PEG to patients up to 55 years of age with no deaths reported as a result of PEG toxicity⁹. Furthermore, advanced age was not associated with hyperbilirubinemia in patients treated on the MOAD protocol at our institution which included patients up to 69 years of age⁵. Patel et al. identified obesity as a risk factor for grade ≥ 3 (Tbili $> 3 - 10 \times \text{ULN}$) liver adverse events, with an increased risk for every 5 unit BMI increment (OR: 1.58, p=0.041)⁴. A retrospective analysis also identified patients with BMI ≥ 30 to be at an increased risk of grade ≥ 3 hepatotoxicity, and did not find age to be a risk factor¹⁰. Patients of Hispanic ethnicity, especially those with larger BMI, have also been reported to experience hepatotoxicity more frequently upon retrospective review¹¹. Specific comorbidities including type 2 diabetes mellitus and dyslipidemia have not been evaluated as risk factors for asparaginase toxicity, however like obesity, these are risk factors for non-alcoholic fatty liver disease, and consequently are worth investigating as risk factors for PEG-induced hyperbilirubinemia¹². Hypoalbuminemia is an indicator of nutritional status as well as the capacity of protein synthesis in the liver, and therefore may also be an indicator of poor PEG tolerance. Anecdotally, at our institution, we have observed significant hyperbilirubinemia in relapsed/refractory patients treated with PEG post allogeneic stem cell transplantation (alloSCT), potentially making transplant another risk factor. The mechanism in which PEG leads to hepatotoxicity is a result of protein derangements caused by glutamine deficiency and impairment of mitochondrial β -oxidation¹³⁻¹⁵. Glutamine depletion results in increased cellular stress and premature restoration of protein synthesis resulting in increased inflammation and cell death^{14,15}. Impaired mitochondrial β -oxidation prevents oxidation of long-chain fatty acids which results in fatty acid and triglyceride accumulation, leading to steatosis¹⁶. Evidence of steatosis has been reported in both pediatric and adult patients treated with asparaginase, indicating this toxicity is not limited only to adults^{17,18}. This protocol will investigate the use of levocarnitine for treatment of PEG-induced hyperbilirubinemia specified as Tbili $> 3 \times \text{ULN}$.

2.1.2 Inotuzumab ozogamicin hepatotoxicity

In an effort to improve efficacy as well as treatment related mortality, novel therapies, especially monoclonal antibodies, are being investigated for the treatment of adult patients with ALL. Inotuzumab ozogamicin is one such monoclonal antibody. Inotuzumab ozogamicin (INO) is an immunoconjugate consisting of humanized IgG4 anti-CD22 antibody linked via an acid-hydrolysable butanoic acid linker to a derivative of calicheamicin, N-acetyl- γ -calicheamicin dimethyl hydrazide. Calicheamicin is a natural product of *Micromonospora echinospora calicensis* and is the most potent member of the enediyne class of DNA-damaging agents¹⁹. INO targets the B-cell receptor CD22 and upon binding, the INO/CD-22 complex is rapidly internalized, calicheamicin is activated intracellularly, and induces double-stranded DNA breaks through DNA binding, impairing transcription and inducing

apoptosis^{19,20}. INO is a desirable immunoconjugate due to the high prevalence of CD22 expression on ALL cell lines as well as its observed clinical efficacy. The toxicity profile of INO includes hepatotoxicity, hyperbilirubinemia, and veno-occlusive disease (VOD) especially in patients undergoing alloSCT after treatment with INO²¹. The mechanism by which INO leads to VOD is thought to be similar to that of gemtuzumab ozogamicin, another calicheamicin immunoconjugate²². VOD may be due to direct injury to endothelial cells of the hepatic arteriole by calicheamicin. This injury triggers an inflammatory cascade which results in a pro-thrombotic and hypofibrinolytic state, similar to what is reported in patients undergoing alloSCT with dual-alkylator conditioning regimens. Furthermore, CD22 expression on sinusoidal endothelial cells may also lead to the uptake of INO and consequently result in sinusoidal damage. Due to the hepatic stress induced by INO, levocarnitine may be a possible treatment in patients experiencing hyperbilirubinemia due to this agent.

2.2 Levocarnitine and Vitamin B Complex

2.2.1 Description

Levocarnitine is a naturally occurring amino acid that acts as a carrier molecule in the transport of long-chain fatty acids across the inner mitochondrial membrane. The shuttling of long-chain fatty acids across the mitochondria allows for oxidation and energy production. Levocarnitine is obtained through dietary consumption and is also biosynthesized. The biosynthesis requires lysine, methionine, niacin, vitamin B6, vitamin C, and iron.

Vitamin B complex is a dietary supplement composed of thiamine (B1) 3 mg; riboflavin (B2) 3mg; niacin (B3) 20 mg; pyridoxine HCl (B6) 0.5 mg; cyanocobalamin (B12) 1 mcg; pantothenic acid 5 mg per capsule and may be used for patients with nutritional deficiencies.

2.2.2 Rationale for the use of levocarnitine and vitamin B complex for treatment of hyperbilirubinemia

Treatment with both PEG and INO can result in significant hepatotoxicity. In animal models, levocarnitine has demonstrated efficacy in normalizing liver enzyme elevations seen in asparaginase damaged steatotic liver²³. Furthermore, levocarnitine deficiency has been observed as a risk factor for valproic acid liver toxicity, which is thought to also be caused by impaired mitochondrial β -oxidation²⁴. The combination of levocarnitine and vitamin B complex has only been reported in a retrospective manner for the treatment of PEG-induced hyperbilirubinemia²⁵⁻²⁸, however due to the success in this setting and low side effect profile associated with this intervention, it is warranted to investigate the use of these agents to treat hyperbilirubinemia due to either PEG or INO. Levocarnitine and vitamin B complex will be initiated for Tbili > 3xULN. Initiating treatment earlier can hopefully prevent the severity of hyperbilirubinemia that has been reported with PEG. Furthermore, despite an effort to identify patients at risk of developing hyperbilirubinemia after treatment with PEG, we are unaware of any intervention that has been done to try to prevent this toxicity other than dose reduction or avoidance of the agent altogether.

3.0 Drug Information

3.1 Levocarnitine²⁹⁻³¹

3.1.1 Product description

Levocarnitine is a white crystalline, hygroscopic powder. It is readily soluble in water, hot alcohol, and insoluble in acetone. The chemical name of levocarnitine is 3-carboxy-2(R)-hydroxy-N,N,N-trimethyl-1-propanaminium, inner salt.

3.1.2 Storage and handling

Levocarnitine vials should be stored at room temperature (25°C) and should be protected from light until use. Unused portions of an opened vial should be discarded, as the formulation does not contain a preservative. Once diluted, levocarnitine solution may be stored at room temperature (25°C) for up to 24 hours when mixed in NS or LR in PVC bags

Levocarnitine tablets and oral solution should be stored at room temperature (25°C). The oral solution should be protected from light.

3.1.3 How supplied

Levocarnitine injection is a sterile aqueous solution containing 1 g of levocarnitine per single-dose 5mL vial adjusted to a pH of 6.0-6.5 with hydrochloric acid or sodium hydroxide. Each carton contains 5 single-dose 5mL vials.

Levocarnitine is also available in oral dosage forms including tablets, oral solution, and sugar-free oral solution. 330 mg tablets are white, round compressed tablets debossed "cor" over "160" on one side, and the other side is plain. Tablets are supplied in blister packs of 1-tablets, in boxes of 90 tablets. Levocarnitine oral solution is supplied in 118 mL (4 FL. OZ.) multiple-unit plastic containers that are packaged 24 per case. Sugar-Free Oral Solution is supplied in 118 mL (4 FL. OZ.) multiple-unit plastic containers that are packaged 24 per case.

3.1.4 Route of administration and pharmacokinetics

Levocarnitine can be administered both intravenously (IV) and orally. IV levocarnitine will be administered as an IV push over 2-3 minutes per standard of care, in accordance with MD Anderson Cancer Center IV push guidelines. Following IV administration, approximately 76% of the dose was excreted in the urine during the first 24 hours after administration. The plasma concentration profiles following IV administration is described as a two-compartment model where the mean distribution half-life was estimated at 0.585 hours and mean apparent terminal elimination half-life was 17.4 hours. Total body clearance of levocarnitine was a mean of 4.0 L/h. Levocarnitine is not plasma protein bound.

Oral levocarnitine tablets and solution were found to be bio-equivalent with maximum plasma concentration (Cmax) approximately 80 umol/L and time to maximum plasma concentration (Tmax) occurred at 3.3 hours. The absolute bioavailability of oral levocarnitine is poor and was found to be $15.1 \pm 5.3\%$ for tablets and $15.9 \pm 4.9\%$ for the oral solution.

After treatment with oral levocarnitine, major metabolites found were trimethylamine N-oxide, primarily in urine (8% to 49% of the administered dose) and [3H]- γ -butyrobetaine, primarily in feces (0.44% to 45% of the administered dose). Urinary excretion of levocarnitine was about 4 to 8% of the dose. Fecal excretion of total carnitine was less than 1% of the administered dose.

Intravenous levocarnitine supplementation has been studied in patients with end-stage renal disease receiving hemodialysis and has been shown to increase carnitine concentrations in this population

when administered at doses ranging from 10 mg/kg to 40 mg/kg 3 times weekly following dialysis. Chronic, oral supplementation has not been evaluated in patients with severe renal impairment or ESRD. Chronic oral supplementation may result in accumulation of renally excreted metabolites trimethylamine (TMA) and trimethylamine-N-oxide (TMAO).

3.1.5 Availability

Levocarnitine is FDA approved and commercially available. Commercial supply will be used.

3.1.6 Agent destruction and return

Unused/expired drug will be disposed of onsite according to institutional guidelines

3.1.7 Warnings and precautions

3.1.7.1 Embryo-fetal toxicity: levocarnitine is pregnancy category B. Reproductive studies performed in rats and rabbits at doses up to 3.8 times the human dose on the basis of surface area have not revealed any evidence of impaired fertility or harm to the fetus due to levocarnitine. There are no adequate and well controlled studies in pregnant women, therefore should only be used during pregnancy if necessary.

Levocarnitine has not been studied in nursing mothers. Studies in cows indicate an increased concentration of levocarnitine in milk following exogenous levocarnitine administration. Nursing mothers receiving levocarnitine should weigh the risks to the child of excess carnitine intake against the potential benefits of supplementation.

Pregnant and nursing mothers will be excluded from this study.

3.1.7.2 Adverse events: Transient nausea and vomiting have been observed with oral and intravenous levocarnitine use. Various mild gastrointestinal complaints including transient nausea, vomiting, abdominal cramps, and diarrhea have been reported with long-term use of oral levocarnitine. These adverse reactions typically resolve with dose reduction.

Seizures have been reported in patients with and without prior seizure activity and in patients with pre-existing seizure activity, an increase in seizure frequency and/or severity has been reported.

Adverse events with a frequency of $\geq 5\%$ regardless of causality by body system reported are listed in appendix I.

3.1.7.2 Overdosage: No reports of toxicity from levocarnitine overdose have been reported.

Levocarnitine is easily removed from the plasma by dialysis. Large doses of the oral formulations may cause diarrhea.

3.2 Vitamin B Complex

3.2.1 Product description

Vitamin B complex is a softgel capsule composed of thiamine (B1) 3 mg; riboflavin (B2) 3mg; niacin (B3) 20 mg; pyridoxine HCl (B6) 0.5 mg; cyanocobalamin (B12) 1 mcg; pantothenic acid 5 mg

3.2.2 Storage and handling

Vitamin B complex capsules should be stored between 15°C and 30°C.

3.2.3 How supplied

Vitamin B complex capsules are softgel capsules supplied in bottles of 100.

3.2.4 Availability

Vitamin B complex is FDA approved and commercially available. Commercial supply will be used.

3.2.5 Agent destruction and return

Unused/expired drug will be disposed of onsite according to institutional guidelines

4.0 Study Design

This is an open-label, two-arm, phase II clinical study.

5.0 Patient Eligibility

Inclusion Criteria:

1. Patients at least 12 years of age
2. Patients with a diagnosis of ALL who are receiving treatment with PEG-asparaginase or inotuzumab ozogamicin with Tbili >3xULN
3. Signed informed consent.

Exclusion criteria:

1. Pregnant or nursing women
2. Known hypersensitivity to levocarnitine or vitamin B complex

6.0 Treatment Plan

6.1 General

All patients will be registered with the Data Management Office PDMS/CORE system.

Treatment with levocarnitine and vitamin B complex will be initiated when total bilirubin is >3xULN. Treatment will consist of IV levocarnitine 50 mg/kg loading dose (maximum 3000 mg) followed by 50 mg/kg/day divided every 6 hours beginning 6 hours after the loading dose was administered. Levocarnitine dose may be increased by 50 mg/kg/day to a maximum of 150 mg/kg/day divided every 6 hours (maximum 3000 mg per dose) if no improvement in total bilirubin after 2 consecutive days of treatment at each dose level. See Table 1 for dosing levels. Treatment will continue until total bilirubin is \leq 1.5 x the upper limit of normal (ULN) or at least a 50% reduction in peak total bilirubin is achieved. If hyperbilirubinemia recurs (Tbili >3xULN), levocarnitine and vitamin B may be reinitiated at the previous dose level and continued until Tbili \leq 1.5 x ULN or at least a 50% reduction in peak total bilirubin is achieved. It is preferred that the patient continue to receive treatment as inpatient. If the treating physician deems patient appropriate for discharge prior to achieving a Tbili of \leq 1.5 ULN or at least a 50% reduction in peak total bilirubin, it is recommended for patient to continue IV levocarnitine as an outpatient. It is recommended for patient to continue IV levocarnitine as an outpatient at the same inpatient dosage divided twice daily (maximum 3000mg per dose). If patient is unable to continue IV levocarnitine as an outpatient, it is recommended the patient receive levocarnitine 990 mg by mouth three times daily until Tbili of \leq 1.5 ULN or at least a 50% reduction in

peak total bilirubin is achieved. Vitamin B complex 1 capsule will be administered by mouth twice daily until Tbili of \leq 1.5 ULN or at least a 50% reduction in peak total bilirubin is achieved. Patients who do not achieve a response within the timeframe of interest may continue to receive protocol medications including levocarnitine and vitamin B complex if there is clinical benefit, and deemed in best interest of the patient by the treating physician.

Patients who are re-challenged with inotuzumab or PEG-asparaginase after receiving treatment for hyperbilirubinemia may continue levocarnitine and vitamin B capsules by mouth at the discretion of the treating physician. If hyperbilirubinemia (Tbili >3 xULN) occurs, patients should receive levocarnitine and vitamin B complex starting at dose level 1 and escalate to a maximum of 150 mg/kg/day according to the recommendations above. Patients will remain on study for 30 days after their last dose of either PEG-asparaginase or inotuzumab.

Intravenous levocarnitine will be administered as an IV push over 2-3 minutes per standard of care, in accordance with MD Anderson Cancer Center IV push guidelines. Levocarnitine oral solution may be dissolved in drink or other liquid food. Oral tablets and oral solution should be administered during or following a meal. Oral solution should be consumed slowly to maximize tolerance. Missed or vomited doses of the oral tablets or solution will not be made up.

Patients will receive vitamin B complex capsules composed of: thiamine (B1) 3 mg; riboflavin (B2) 3mg; niacin (B3) 20 mg; pyridoxine HCl (B6) 0.5 mg; cyanocobalamin (B12) 1 mcg; pantothenic acid 5 mg per capsule while inpatient. Patients may receive any commercially available vitamin B complex product while outpatient even if the composition differs from what is described above. Missed or vomited doses will not be made up.

Table 1. Levocarnitine dose levels:

| Dose level | IV levocarnitine dose |
|------------|-------------------------------------|
| 1 | 50 mg/kg/day divided every 6 hours |
| 2 | 100 mg/kg/day divided every 6 hours |
| 3 | 150 mg/kg/day divided every 6 hours |

6.1.1 Compatibility:

Levocarnitine injection solution is compatible and stable when mixed in parenteral solutions of Sodium Chloride 0.9% or Lactated Ringer's in concentrations ranging from 250 mg/500 mL (0.5 mg/mL) to 4200 mg/500 mL (8.0 mg/mL)

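### Levocarnitine is to continue until bilirubin responds, and may be escalated on bilirubin alone, with no written exception for levocarnitine toxicity

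*Combined protocol and SAP*

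**What the plan says.** Section 6.1 gives a loading dose and then 50 mg/kg/day. On escalation it says "Levocarnitine dose may be increased by 50 mg/kg/day to a maximum of 150 mg/kg/day divided every 6 hours", subject to a 3000 mg cap per dose and to no bilirubin improvement after two consecutive days at the level. The end of treatment is set by bilirubin: "Treatment will continue until total bilirubin is" at or below 1.5 times ULN, or has fallen by at least half from its peak. On recurrence, "levocarnitine and vitamin B may be reinitiated at the previous dose level". If hyperbilirubinemia follows re-challenge with the anticancer drug, "patients should receive levocarnitine and vitamin B complex starting at dose level 1 and escalate to a maximum of 150 mg/kg/day".

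One sentence in 6.1 brings in clinical judgement about continuing: patients without a response in the time allowed may stay on treatment "if there is clinical benefit, and deemed in best interest of the patient by the treating physician".

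Section 3.1.7 warns: "Seizures have been reported in patients with and without prior seizure activity". For patients with pre-existing seizure activity it adds that "an increase in seizure frequency and/or severity has been reported". It also notes that gastrointestinal reactions usually settle when the dose is lowered. In section 5.0 the only exclusions are pregnancy or nursing and "Known hypersensitivity to levocarnitine or vitamin B complex".

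The Statistical Considerations require at least five consecutive days of levocarnitine before a patient counts as evaluable for response.

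**The concern.** The protocol names a neurological hazard and a dose-responsive gastrointestinal one, but its dosing rules look only at bilirubin. Read literally, a patient with a levocarnitine-related reaction inside the 11-day or 7-day window goes on receiving the drug until bilirubin responds, and receives it again if hyperbilirubinemia returns after re-challenge. Nothing requires a higher dose in such a patient, but nothing rules one out. Physicians facing the same event may continue, escalate, reduce or stop, which leaves protection uneven and makes the tolerability objective (1.2.2) harder to interpret.

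Any toxicity rule also has a consequence for the primary endpoint. A patient held or stopped before five consecutive days is no longer evaluable for response, so poor tolerability would drop out of the response rate without being seen.

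**Working it through.** **1. Is there a toxicity rule anywhere?** The places where one could sit:
- 6.1, escalation: bilirubin criterion and per-dose cap only; permissive.
- 6.1, continuation: bilirubin criterion only; directive.
- 6.1, recurrence: permissive. Re-challenge: worded as what patients should receive, with no exception for an earlier reaction.
- 6.1, clinical benefit and best interest: applies only after the response window has passed without response.
- 3.1.7: warnings and a descriptive remark on dose reduction; no instruction.
- 10.0: investigator approval of dose changes under an outside physician; no criterion for making one.
- Statistical Considerations: stopping for futility on response; descriptive safety summaries.
- Reporting Requirements: convulsions appear as an example of an important medical event, and SAEs go to the IND Office within 5 working days; nothing on dose. Appendix C, cited there, is not in the supplied text; it is cited for adverse event recording and reporting.

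None of these holds, reduces, stops or blocks escalation of levocarnitine for toxicity.

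**2. Dose, as context only.** The only studied IV range in patients that the documents state is 10 to 40 mg/kg three times weekly after dialysis (3.1.4), so at most 40 × 3 = 120 mg/kg/week. Level 1 is 50 × 7 = 350 mg/kg/week, or 2.9 times that. The fastest escalation in the 7-day inotuzumab window is a 50 mg/kg load, two days at 50, two at 100 and three at 150: 50 + 100 + 200 + 450 = 800 mg/kg, and 800/120 = 6.7 times. This compares dose, not exposure, since dialysis patients clear the drug differently.

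**3. The plan's design figures.** Stop if ≤6/19, reject if ≥17/39, exact binomial: rejection probability 0.0455 at a 30% response rate and 0.8036 at 50%; early stopping under the null 0.666. These agree with the plan.

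**4. The five-day rule and early responders.** Treatment ends at response, so a patient who responds by the end of day 4 need not reach five days. Inputs: the plan's exponential model and its target medians of 11 and 7 days, which give 50% response by the end of each window.
- PEG-asparaginase: response by day 4 is 1 − 2^(−4/11) = 0.223. With these patients left out, (0.5 − 0.223)/(1 − 0.223) = 0.36.
- Inotuzumab: 1 − 2^(−4/7) = 0.327. With these patients left out, (0.5 − 0.327)/(1 − 0.327) = 0.26.

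**5. Power if early toxicity stops are counted.** Let f be the share stopped early (assumed; the documents give no rate). The overall response rate is 0.5(1 − f) + r·f, where r is the response rate among those stopped. Taking r = 0.30 uses the plan's rate without treatment; r = 0 is the worst case.

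| f | Response rate, r = 0.30 | Power | Response rate, r = 0 | Power |
|---|---|---|---|---|
| 0 | 0.500 | 80.4% | 0.500 | 80.4% |
| 1% | 0.498 | 79.7% | 0.495 | 78.7% |
| 5% | 0.490 | 76.9% | 0.475 | 71.0% |
| 10% | 0.480 | 73.0% | 0.450 | 59.9% |

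**The case against.** The strongest reply is that the protocol is silent on toxicity and does not direct dosing through it. Escalation and restart after recurrence are optional. Safety is assessed after a single dose and evaluability needs five days, so the plan foresees that some patients stop early. Section 10.0 foresees dose changes. Section 3.1.7 reports no toxicity from overdose and easy removal by dialysis, and 2.2.2 describes a low side-effect profile. A physician would very probably stop after a seizure.

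Most of this stands and limits the severity. None of it is a dosing rule, however, and the best-interest wording starts only after the window closes.

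Three stronger readings are tempting, and the documents do not support them:
- *The protocol forces higher doses on patients with toxicity.* It does not; the wording is permissive.
- *Appendix I shows a dose-related harm.* Diarrhea is 35% in the highest-dose column against 19% on placebo (about 12/34 against 12/63, Fisher p = 0.089). That is one row among many. Hypotension and dyspnea, each 3% against 19%, run the other way (p = 0.030), and pooled diarrhea is 16% against 19%. Seizure is not among the events listed at 5% or more.
- *Patients receive 8.75 times the studied dose.* That needs a full week at level 3 (1050/120), which cannot occur within the 7-day inotuzumab window.

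It can also be said that the loss of early responders is a separate defect of the five-day rule. That is fair: it exists with or without a toxicity rule. It belongs here because the same sentence must change for both reasons.

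**Conclusion.** The point holds as a modest safety weakness. The directive continuation sentence and the re-challenge sentence lack a toxicity exception, and the written escalation criterion ignores tolerability, although the protocol itself warns of seizures. How many patients this would affect cannot be estimated from the documents. A reader might infer that the protocol intends dosing to go on after a seizure; the text shows only that the case is not addressed.

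The numerical consequence lies in the evaluability rule. Read literally, it could reduce a true 50% response rate to 36% or 26% by losing early responders. This assumes that the exponential model and target medians hold and that treatment does stop at response. In the other direction, it removes toxicity stops from the denominator, by an unknown amount.

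**What to change.** **Section 6.1.** Allow escalation only if bilirubin has not improved and there is no ongoing levocarnitine-related toxicity at or above a CTCAE v4.0 grade that the investigators set. For such toxicity, hold or step down one level; from level 1, hold. Stop levocarnitine for a new or worsened seizure judged possibly related. A permanent stop for any seizure whatever its cause is a clinical choice that the documents do not settle. Make the continuation, recurrence and re-challenge sentences subject to these rules.

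**Statistical Considerations.** Replace the five-consecutive-day rule. Patients held or stopped for toxicity before day 5, and patients who stop before day 5 because they responded, stay in the denominator and are classed by the response definition.

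**Cost.** A few sentences and no new tests, since CTCAE grading and investigator attribution are already required. A few patients will not escalate. Attribution will be imprecise: Appendix I shows 19% diarrhea and 16% vomiting on placebo. Counting early toxicity stops lowers power as tabulated above, slightly if they are rare; keeping early responders works the other way.
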